**[REDACTED]**

f Concomitant medication with a start date after the visit window of Day 100 (Day 107) will be collected in MSB-GVDH002.

Concomitant medication with a start date before the visit window of Day 100 (Day 106) will be collected in MSB-GVDH001.

g Total number of units transfused of blood product will be recorded in the eCRF during study. Transfusion with a start date after the visit window of Day 100 (Day 107) will be collected in MSB-GVDH002. Transfusion with a start date before the visit window of Day 100 (Day 106) will be collected in MSB-GVDH001

■ [REDACTED]  
■ [REDACTED]  
■ [REDACTED]  
■ [REDACTED]

j Pregnancy test will be performed on all females of childbearing potential (subjects  $\geq 10$  years of age). Guidance on childbearing potential and pregnancy testing is located in [Appendix 7](#).

k All AEs will be collected in this study. Adverse events with an onset date after the visit window of Day 100 (Day 107 – as allowed in protocol MSB-GVHD001) will be collected in MSB-GVHD002.

Adverse events with an onset date before the visit window of Day 100 (Day 106 – as allowed in protocol MSB-GVHD001) will be collected in MSB-GVHD001

l CT scans and MRI are optional and may be omitted at the discretion of the Investigator.

### 4.3 Study Sites

This study will be conducted in approximately 40 different sites.

## 5. STUDY POPULATION

### 5.1 Enrollment

The study plans to evaluate only those subjects who participated in Protocol MSB-GVHD001. All subjects who enrolled in Protocol MSB-GVHD001 and who meet the inclusion and exclusion criteria for MSB-GVHD002 will be enrolled in Protocol MSB-GVHD002, using the same subject number they received in MSB-GVHD001. Subjects will be followed through 180 days after initial therapy with remestemcel-L.

### 5.2 Eligibility Criteria

#### 5.2.1 Inclusion Criteria

Subjects are eligible for the study if all of the following criteria are met:

1. Subjects must have participated in Protocol MSB-GVHD001 and have received at least one infusion of remestemcel-L.
2. Subject or subject's authorized representative must provide written informed consent. Assent, if applicable, must also be collected when required by the IRB/EC.
3. Female subjects of childbearing potential ( $\geq 10$  years of age) ([Appendix 7](#)) must use a medically accepted method of contraception and must agree to continue use of this method for the duration of the study and for the follow-up time period. Acceptable methods of contraception include abstinence, barrier method with spermicide, intrauterine device (IUD), or steroidal contraceptive (oral, transdermal, implanted, and injected) in conjunction with a barrier method.
4. The subject must be willing and able to comply with study procedures, remain at the clinic as required during the study protocol, and return to the clinic for the follow-up evaluations as specified in this protocol.

### 5.2.2 Exclusion Criteria

Subjects are eligible for the study as long as the following criteria are not met:

1. The investigator believes it to be in the best interest of the subject not to participate in the safety follow up study.
2. Subject has participated or is currently participating in any autologous or allogeneic stem cell or gene therapy study for the treatment of aGVHD. Patients participating in investigative protocols aimed at modification of the transplant graft (such as T cell depletion) or aimed at modification of the conditioning regimen will be allowed in the study.

### 5.3 Premature Subject Withdrawal

Subjects may voluntarily withdraw from the study for any reason at any time. Subjects may be also considered withdrawn if they state an intention to withdraw, fail to return for visits, or become lost to follow-up.

At a minimum, the following should be collected when a subject withdraws:

- The reason the subject discontinued
- The date of the last assessment and/or contact
- Adverse events (AEs) , including concomitant medications used to treat AEs
- Final (end of study) assessments.

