### 5.4 Lost to Follow-Up

A subject is considered to have been lost to follow-up if he/she is unable to be contacted by the investigator post randomization after reasonable efforts have been made to contact the subject. The investigator should show “due diligence” by documenting in the source documents steps taken to contact the subject, e.g., dates of telephone calls or registered letters. The end of participation for a subject lost to follow-up is the date of the last known contact (e.g., visit or telephone contact).

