## 6. STUDY PROCEDURE

### 6.1 Visit Schedule and Assessments

Table 6 lists all planned assessments, which are marked with an “X” when the visits are performed. Subjects should be seen for all visits on the designated day or at a time that is as close as possible to the designated day. The study assessment schedule in Table 6 outlines all procedures to be performed on subjects at the scheduled visits.

In order to minimize variability in evaluations, ideally, the same individuals should perform the same tests on all the subjects at a given trial site.

The following assessments and procedures will be performed at study visits:

- Informed consent. Subject may be consented on MSB-GVHD002 simultaneously when being provided with the MSB-GVHD001 consent, or at any visit up through Day 180 ( $\pm$  7 days). If the IRB/EC has not yet approved the consent for MSB-GVHD002 at Day 100 (MSB-GVHD001), the Investigator should make all efforts to have the IRB/EC approved consent for MSB-GVHD002 presented to the subject no later than Day 180 ( $\pm$  7 days). See Section 6.3 for additional information about handling of visits from Day 100 through Day 160 when an IRB/EC approved consent is not available.
- Review of inclusion / exclusion criteria
- Physical examination
- Height and weight
- Vital signs (heart rate [HR], blood pressure [BP], temperature, and respiratory rate [RR])
- GVHD assessment (skin, lower GI, upper GI, liver) using the same method as that of MSB-GVHD001
- O2 saturation by pulse oximetry (SaO2/SAT)
- Adverse event (AE) assessment
- Incidence of chronic GVHD (cGVHD) (Appendix 8)
- Survival status
- Information on hospitalization status (namely the date of hospitalization)
- Steroid dose(s)
- Prior and concomitant medications

- Laboratory assessments
  - Hematology (including CMV, please see [Table 6](#) for details)
  - Serum chemistry
  - Urinalysis
- [REDACTED]
- Optional CT scan or MRI of the chest, abdomen, and pelvis at the discretion of the investigator. Scans may contribute information with regard to baseline disease burden and may also provide baseline for evaluation of future possible ectopic tissue formation. For CT, use intravenous (IV) contrast; if IV is contraindicated for any reason, oral is acceptable even in the presence of GI GVHD.
- 12-Lead ECG
- [REDACTED]
- [REDACTED]
- [REDACTED]

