#### **9.4.2 Survival to Day 180**

The number of subjects alive, deceased, lost to follow-up, or withdrawn from Day 0 (Protocol MSB-GVHD001) to Day 180 (Protocol MSB-GVHD002) will be summarized in a Subject Disposition table. For subjects who died, the time to event will be calculated from date of transplant, date of aGVHD onset, and date of treatment initiation. All other subjects will be censored and survival time will be calculated from the date of transplant, date of aGVHD onset, or date of treatment initiation to the date of last contact.

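### No Day 180 vital status check is required for children who stop attending, so Kaplan-Meier survival can be overstated and deaths undercounted

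*Combined protocol and SAP*

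**What the plan says.** Survival through Day 180 is one of the four primary safety parameters (Section 4.1.1). Survival at 180 days is the first secondary endpoint (Section 4.1.2).

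- **Withdrawal (Section 5.3).** "Subjects may be also considered withdrawn if they state an intention to withdraw, fail to return for visits, or become lost to follow-up". The wording is permissive, but it gives three separate routes, so a child who is reachable and merely absent can be classed as withdrawn. The minimum data collected on withdrawal are the reason, "The date of the last assessment and/or contact", adverse events with the medication used for them, and "Final (end of study) assessments". Day 180 vital status is not an item.
- **Loss to follow-up (Section 5.4).** The site shows diligence by "documenting in the source documents steps taken to contact the subject, e.g., dates of telephone calls or registered letters". The section closes: "The end of participation for a subject lost to follow-up is the date of the last known contact".
- **Assessments (Section 6.1).** "Survival status" is listed among the items performed at study visits.
- **Time to death (Section 9.4.2).** Deaths are events. For the rest: "All other subjects will be censored and survival time will be calculated from the date of transplant", or from aGVHD onset or start of treatment, up to the date of last contact.
- **Day 180 status (Section 9.5.1).** Survival, non-survival and missing are shown as separate categories. In the table of Day 28 response against Day 180 survival, percentages use all subjects, including those whose survival is unknown. Kaplan-Meier curves and a log-rank test by Day 28 responder status are planned, with a CMH test and an odds ratio.
- **Missing values (Section 9.9).** Nothing is imputed for safety analyses in general. Endpoint-specific rules are left to the SAP.

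**The concern.** Death is the outcome that matters most here, and it can be established without a clinic visit. The plan nevertheless ties it to attendance. In these children, missing visits may well go with deterioration, relapse or transfer of care. Censoring at last contact assumes that a child who leaves has the same later risk of death as one who stays. If that is wrong, the Kaplan-Meier curve is too high, and deaths after the last contact can be lost from a study whose purpose is safety follow-up.

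Section 6.5.4 shows that the protocol can prevent this kind of loss: it says that escalating therapy is not withdrawal and keeps those children under assessment. Missed visits have no such protection. The SAP cannot repair the gap later, because no analysis rule recovers a status that sites were never told to collect.

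**Working it through.** The documents state no sample size, dropout rate or survival rate for this study, so there is no planned figure to reproduce. Every rate below is an assumption, used only to show direction and size.

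**Set-up, Day 100 to Day 180.** Let *s* be survival in children who stay, *d* the share who stop attending, and *k* the ratio of their hazard of death to that of children who stay. Their survival is *u* = *s*^*k*. Assume first that they leave just after Day 100.

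- True survival = (1 − *d*)·*s* + *d*·*u*
- Kaplan-Meier with leavers censored = *s*, so its bias = *d*·(*s* − *u*)
- Survivors tabulated on all subjects = (1 − *d*)·*s*, which is too low by *d*·*u*
- Deaths tabulated on all subjects = (1 − *d*)·(1 − *s*), which is too low by *d*·(1 − *u*)

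**One case in full.** With *s* = 85%, *d* = 10% and *k* = 3, *u* = 0.85³ = 61.4%. True survival = 0.90 × 85% + 0.10 × 61.4% = 82.6%. Kaplan-Meier shows 85.0%, which is 2.4 points too high. Tabulated survivors = 0.90 × 85% = 76.5%, which is 6.1 points too low. Tabulated deaths = 0.90 × 15% = 13.5%, against a true 17.4%.

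| *s* | *d* | *k* | True survival | Kaplan-Meier | Bias | Survivors tabulated | Deaths tabulated | True deaths |
|---|---|---|---|---|---|---|---|---|
| 85% | 10% | 1 | 85.0 | 85.0 | 0 | 76.5 | 13.5 | 15.0 |
| 85% | 10% | 3 | 82.6 | 85.0 | +2.4 | 76.5 | 13.5 | 17.4 |
| 85% | 20% | 3 | 80.3 | 85.0 | +4.7 | 68.0 | 12.0 | 19.7 |
| 70% | 20% | 3 | 62.9 | 70.0 | +7.1 | 56.0 | 24.0 | 37.1 |

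Across *s* of 70% or 85%, *d* of 5 to 20% and *k* of 1 to 3, the Kaplan-Meier bias is 0 to 7.1 points.

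**A second set of assumptions, mortality stated directly.** Take 90% survival in those who stay.

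- 10% leave early and 40% of them die: 0.90 × 90% + 0.10 × 60% = 87%, against 90% shown.
- 20% leave early and 40% of them die: 0.80 × 90% + 0.20 × 60% = 84%, against 90%.
- Mildest corner, 5% leaving and 30% dying: 0.95 × 90% + 0.05 × 70% = 89%, a bias of 1 point.
- Worst corner, 20% leaving and 50% dying: 0.80 × 90% + 0.20 × 50% = 82%, a bias of 8 points.

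**Dropout spread over the period.** In a simulation with leaving times uniform over Day 100 to 180, *s* = 85% and the hazard tripled after leaving, the Kaplan-Meier bias was about +0.6, +1.2 and +2.4 points at 5, 10 and 20% dropout. This is smaller than with early dropout, because less time remains unobserved.

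**Responders against non-responders.** The bias in each group is that group's own *d*·(*s* − *u*). If it is larger among non-responders, their curve is lifted more and the gap narrows. If it is larger among responders, the gap widens. The documents do not settle which.

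**The case against.** A reader might infer three stronger conclusions. The documents support none of them.

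1. *Survival is overstated throughout.* It is not. Section 9.5.1 shows missing status as its own category and keeps those children in the denominator of the response-by-survival table. A child of unknown status is not counted as a survivor, so that percentage errs low. The overstatement is confined to Kaplan-Meier. What stands is that the same table understates deaths whenever any child of unknown status has died, and that the two displays err in opposite directions. How unknown status enters the CMH test and the odds ratio is not stated.

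2. *Vital status is not pursued at all.* Section 5.4 requires documented contact attempts. Section 6.3 discourages missed visits and has sites notify the sponsor of them. Section 8 requires serious adverse events to be followed to resolution or stabilisation. Section 5.3 asks for final assessments. Section 9.4.2 censors at last contact, and Section 5.4 counts a telephone call as contact, so a child reached on Day 180 already contributes to Day 180. These provisions narrow the gap without closing it. The Section 5.4 efforts decide whether a child is lost, and none of the provisions sets a status check at Day 180 for a child already classed as withdrawn.

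3. *The bias favours the product.* This is not shown. The planned Kaplan-Meier comparison is between Day 28 responders and non-responders. If sicker non-responders leave more often, the association under test is weakened.

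The size can also be challenged fairly. In the second set of assumptions, mortality of 30 to 50% in leavers against 10% in the rest implies hazard ratios of about 3.4 (ln 0.7 / ln 0.9) to 6.6 (ln 0.5 / ln 0.9), all with early dropout. The upper figures are corner cases.

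**Conclusion.** The point holds as a gap in data collection. A child who stops attending may be classed as withdrawn, no visible text then requires Day 180 vital status, and survival time ends at last contact. If leaving is linked to prognosis, Kaplan-Meier survival is too high and tabulated deaths are too low. The tabulated survivor percentage is a lower bound, and the responder comparison can move either way.

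On assumed rates, the Kaplan-Meier bias is 0 when dropout is non-informative, about 0.6 to 2.4 points in the spread-dropout case, and about 7 to 8 points with 20% early dropout and high mortality. The direction depends on sicker children leaving, which is plausible here but is not stated in the documents. The size depends on dropout and mortality rates that the documents do not give. This is a worthwhile, inexpensive improvement and does not invalidate the planned survival analysis.

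**What to change.** **Sections 5.3 and 5.4.** State that missing visits is not withdrawal. For every child, including those who stop visits, the site records vital status and any date of death at Day 180, by telephone or from the transplant centre's records, unless that follow-up is itself refused. The check should cover all such children at the same date, so that deaths that happen to come to notice are not counted while living non-attenders are censored early.

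**Sections 9.4.2 and 9.5.1.** Censor before Day 180 only children whose status remains unknown. Report their number by Day 28 response. Add two bounds, with unknowns counted as all dead and as all alive. In the worked case, before any status is recovered, these would be 76.5% and 76.5% + 10% = 86.5%, around a true 82.6%. If every status were obtained, the Kaplan-Meier and tabulated figures would both equal true survival.

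**Cost.** Short protocol and consent wording, and one call or chart check per affected child. No visit or procedure is added.

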### 5.4 Lost to Follow-Up

A subject is considered to have been lost to follow-up if he/she is unable to be contacted by the investigator post randomization after reasonable efforts have been made to contact the subject. The investigator should show “due diligence” by documenting in the source documents steps taken to contact the subject, e.g., dates of telephone calls or registered letters. The end of participation for a subject lost to follow-up is the date of the last known contact (e.g., visit or telephone contact).

### 5.5 End of Study

The end of study is defined as any one of the following, whichever occurs first:

- The date of the last scheduled visit for the last subject
- The date of death of the last subject
- The date of withdrawal of the last subject.

Individual subjects will be deemed to have completed study when they have completed all required protocol procedures and assessments. For subjects with ongoing adverse events at the last scheduled visit, the end of study date will be deemed to be the last scheduled visit date.

## 6. STUDY PROCEDURE

### 6.1 Visit Schedule and Assessments

Table 6 lists all planned assessments, which are marked with an “X” when the visits are performed. Subjects should be seen for all visits on the designated day or at a time that is as close as possible to the designated day. The study assessment schedule in Table 6 outlines all procedures to be performed on subjects at the scheduled visits.

In order to minimize variability in evaluations, ideally, the same individuals should perform the same tests on all the subjects at a given trial site.

The following assessments and procedures will be performed at study visits:

- Informed consent. Subject may be consented on MSB-GVHD002 simultaneously when being provided with the MSB-GVHD001 consent, or at any visit up through Day 180 ( $\pm$  7 days). If the IRB/EC has not yet approved the consent for MSB-GVHD002 at Day 100 (MSB-GVHD001), the Investigator should make all efforts to have the IRB/EC approved consent for MSB-GVHD002 presented to the subject no later than Day 180 ( $\pm$  7 days). See Section 6.3 for additional information about handling of visits from Day 100 through Day 160 when an IRB/EC approved consent is not available.
- Review of inclusion / exclusion criteria
- Physical examination
- Height and weight
- Vital signs (heart rate [HR], blood pressure [BP], temperature, and respiratory rate [RR])
- GVHD assessment (skin, lower GI, upper GI, liver) using the same method as that of MSB-GVHD001
- O2 saturation by pulse oximetry (SaO2/SAT)
- Adverse event (AE) assessment
- Incidence of chronic GVHD (cGVHD) (Appendix 8)
- Survival status
- Information on hospitalization status (namely the date of hospitalization)
- Steroid dose(s)
- Prior and concomitant medications

- Laboratory assessments
  - Hematology (including CMV, please see [Table 6](#) for details)
  - Serum chemistry
  - Urinalysis
- [REDACTED]
- Optional CT scan or MRI of the chest, abdomen, and pelvis at the discretion of the investigator. Scans may contribute information with regard to baseline disease burden and may also provide baseline for evaluation of future possible ectopic tissue formation. For CT, use intravenous (IV) contrast; if IV is contraindicated for any reason, oral is acceptable even in the presence of GI GVHD.
- 12-Lead ECG
- [REDACTED]
- [REDACTED]
- [REDACTED]
- Serum pregnancy test for female subjects  $\geq 10$  years of age (see [Appendix 7](#) for guidance on childbearing potential and pregnancy testing)
- Transfusion (if applicable). Type of transfusion and the number of units will be recorded in the eCRF.

Measurement of all clinical parameters should be performed as described in [Table 6](#). Standard instructions for determining these parameters are provided in the following sections.

### 6.1.1 Safety Assessments

Many of the study assessments scheduled for Day 100 will be completed during the MSB-GVHD001 protocol and, therefore, will not be completed at the Day 100 visit for this protocol.

#### 6.1.1.1 Physical Examination

A physical examination, including but not limited to, examination for evidence of adverse events, will be performed at Day 120, Day 140, Day 160, the end of study/Day 180, and at unscheduled visits as needed.

Information about physical examinations must be available in the source documentation at the study site. Significant new findings made after the Day 100 visit that meet the definition of an AE or SAE must be recorded on the Adverse Event CRF.

### **6.1.1.2 Vital Signs**

Vital sign measurements should be performed at Days 120, 140, 160, End Of Study/Day 180, and at unscheduled visits as needed.

Measurements of vital signs will include sitting systolic blood pressure (SBP), diastolic blood pressure (DBP), heart rate (HR), temperature, and respiratory rate (RR).

Vital signs will be measured after approximately 5 minutes of quiet rest with the subject in a sitting position. Ideally, the site should have a dedicated blood pressure machine and use the same machine and blood pressure measurement method for all subjects during the trial.

### **6.1.1.3 Oxygen Saturation**

Concurrent with vital sign measurements, Oxygen saturation (SaO2/SAT) will be monitored by pulse oximetry. Supplemental oxygen may be administered as needed but should be noted in the source documents

### **6.1.1.4 Height and Weight**

Height and weight measurements should be performed at End of Study/Day 180 or at unscheduled visits as needed.

Measurement of height from a standing position should be performed with the subject's shoes removed, the knees straightened, and head held upright. For infants, height should be measured lying down, and measurements should be recorded as recumbent length.

Measurement of weight should be performed without shoes or extra layers of clothing (e.g., sweater or jacket) during the measurement. Subjects should be weighed on the same scales at all visits.

### **6.1.1.5 12-Lead Electrocardiogram (ECG)**

12-lead electrocardiogram (ECG) will be performed at End of Study/Day 180 or at unscheduled visits as needed, to assess any changes in cardiac physiology from prior measurements performed at Day 0 and Day 100 in MSB-GVHD001. Subjects should be in a supine or semi-supine position for at least 5 minutes prior to the recording. The same recording position (supine or semi-supine) and the same equipment should be used for each subject throughout the study.

All ECG tracings must be (1) reviewed by a medically qualified member of the study team, (2) annotated to indicate any clinical finding, (3) signed and dated by the medically qualified member, and (4) filed with the notes for the subjects. ECG parameters will be entered into the CRF, and if any ECG abnormality is associated with an (S)AE, it must be entered in the (S)AE CRF.

Heart rate (HR), pulse rate (PR), QRS and QT durations should also be noted on the CRF along with the ECG parameters.

#### **6.1.1.6 (Serious) Adverse Events**

All (S)AEs, including those considered to have a causal relationship to the IMP, will be collected at each assessment time point. (S)AEs collected will consist of both solicited and events voluntarily reported by the subjects.

